1. INTRODUCTION AND OBSERVATIONS

Osteoarthritis (OA) is the most common form of arthritis that causes degenerative structural change and results in pain and decreased mobility. Samumed, LLC is developing SM04690, a small molecule inhibitor of the Wnt pathway, for the treatment of OA. The purpose of this study is to assess the efficacy, safety and tolerability of three different strengths of SM04690 administered by intra-articular injection into the target knee joint of moderately to severely symptomatic OA subjects.

1.1. Primary Objectives

The primary objective of this study will be to evaluate the change from baseline OA pain in the target knee as assessed by the Western Ontario and McMaster Universities Osteoarthritis Index (WOMAC) pain subscore at Week 13.

1.2. Secondary Objectives

The secondary objectives of this study include:

- Evaluate change from baseline OA pain in the target knee as assessed by the WOMAC pain subscore at Week 26
- Evaluate change from baseline OA function in the target knee as assessed by the WOMAC function subscore at Weeks 13 and 26
- Evaluate change from baseline OA disease activity as assessed by the Patient Global Assessment at Weeks 13 and 26
- Evaluate change from baseline in medial joint space width (JSW) as documented by X-ray of the target knee at Week 26
- Evaluate the safety and tolerability of SM04690 by monitoring for treatment-emergent adverse events (TEAEs)

1.3. Exploratory Objectives

Additional exploratory objectives of this study include:

- Evaluate change from baseline in WOMAC total score for the target knee at Weeks 4, 13, 26, 39 and 52
- Evaluate change from baseline OA pain in the target knee as assessed by the WOMAC pain subscore at Weeks 4, 39 and 52
- Evaluate change from baseline OA function in the target knee as assessed by the WOMAC function subscore at Weeks 4, 39 and 52
- Evaluate change from baseline OA disease activity as assessed by the Patient Global Assessment at Weeks 4, 39 and 52
- Evaluate change from baseline in medial JSW as documented by X-ray of the target knee at Week 52
- Evaluate change from baseline in lateral JSW as documented by X-ray of the target knee at Weeks 26 and 52

- Determine the percentage of Outcome Measures in Rheumatology Clinical Trials (OMERACT)-Osteoarthritis Research Society International (OARSI) responders and “strict” responders at Weeks 4, 13, 26, 39 and 52
- Evaluate change from baseline health-related quality of life (HRQOL) as assessed by the 36-Item Short Form Health Survey (SF-36) at Weeks 4, 13, 26, 39 and 52
- Evaluate change from baseline OA disease activity as assessed by the Physician Global Assessment at Weeks 4, 13, 26, 39 and 52

2. STUDY DESIGN

This study will be a multicenter, randomized, double-blind, placebo-controlled, parallel group study of three different strengths of SM04690 injected into the target knee joint of moderately to severely symptomatic osteoarthritis subjects.

2.1. Sample Size

A sample size of approximately 445 subjects will be randomized at a ratio of 1:1:1:1 (0.03 mg active per 2 mL injection : 0.07 mg active per 2 mL injection : 0.23 mg active per 2 mL injection : placebo). The sample size for this study was based upon accepted statistical practice to establish an acceptable level of precision with respect to treatment effect estimation ([Piantadosi 1997](#)).

To explore possible power expected from this study design, an analysis of covariance regression model was simulated via a Monte Carlo simulation of 1000 replicates. The simulation model estimated a change in WOMAC Pain from baseline comparison between SM04690 and placebo adjusting for baseline WOMAC Pain. The following assumptions were made for the power simulation:

- Sample size of 100 subjects per group,
- Type 1 error rate of 5%,
- WOMAC Pain Baseline average is 11 points [scale 0-20] with a standard deviation of 3,
- WOMAC Pain Baseline is the same for both treatment and placebo groups,
- Treatment change from baseline is -5.8 points, leading to a final score of 5.2 points [scale 0-20]
- Historical placebo change from baseline is -3.5 points, leading to a final score of 7.5 points [scale 0-20]
- Final pain score has standard deviation of 4 and is the same for both treatment and placebo groups, and
- Correlation between baseline and final pain score is 0.1.

The WOMAC Pain subscore parameters were based upon observed data from the 0.07 mg group in SM04690-01. Based upon these assumptions, SM04690-OA-02 is estimated to have 95.8% power.

A simulation model for WOMAC Function was also estimated. The following assumptions were made for the power simulation:

- Sample size of 100 subjects per group,
- Type 1 error rate of 5%,
- WOMAC Function Baseline average is 39 points [scale 0-68] with a standard deviation of 11,
- WOMAC Function Baseline is the same for both treatment and placebo groups,
- Treatment change from baseline is -19.5 points, leading to a final score of 19.5 points [scale 0-68]
- Historical placebo change from baseline is -13.5 points, leading to a final score of 25.5 points [scale 0-68]
- Final function score has standard deviation of 15 and is the same for both treatment and placebo groups, and
- Correlation between baseline and final function score is 0.1.

The WOMAC Function subscore parameters were also based upon observed data from the 0.07 mg group in SM04690-01. Based upon these assumptions, SM04690-OA-02 is estimated to have 78.5% power.

No prior data exist for Patient Global Assessment in SM04690-01; no formal power analysis is possible at this time.

2.2. Randomization

Subjects will be randomized 1:1:1:1 (0.03 mg active per 2 mL injection : 0.07 mg active per 2 mL injection : 0.23 mg active per 2 mL injection : placebo) to each dose group using Medidata Balance with a permuted block design stratified by study site. A block size of 8 has been selected for this study.

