3.2. Measures to Minimize Bias

3.2.1. Blinding

This is a double-blind study. Study medication will be provided to the investigational center. The investigational center must identify unblinded personnel who will be responsible for preparing the appropriate dilution of the study medication and who are able to perform the injection of study medication and/or placebo. Study personnel administering or preparing study medication and reference therapy must minimize any contact with the subject following the injection and may not perform any study assessments throughout the duration of the study. On study visit Day 1, subjects will be randomized via the Medidata database.

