3.2.3. Subject Re-screening

Subjects are allowed to be re-screened once. Re-screens are limited to subjects who did not meet inclusion/exclusion criteria due to a transient reason. Transient refers to self-limiting and predictably resolving conditions or acute events (e.g., seasonal allergies, common cold, or otitis media), reversible medical conditions that are successfully treated (e.g., anemia successfully treated by infusion), and/or being unable to comply with study procedures due to administrative convenience (e.g., family issues or attending to a private matter).

Subjects who failed any entry criteria in which no further treatment or spontaneous resolution is expected are not allowed to be re-screened.

Any re-screened subject must be re-consented and will be issued a new subject number. All screening procedures and assessments must be performed at re-screen; no results or data may be used from the previous screen.

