8.4. Accountability of Study Medications

All study medication vials received must be returned and accounted for. All injections prepared and dispensed must also be logged. The log includes the following:

- Subject number and initials
- Date that study medication was prepared/injected
- Quantity dispensed (active vial, vehicle vial, PBS vial, and saline vial)
- Quantity returned (active vial, vehicle vial, PBS vial, and saline vial)

All study medication received, prepared, and dispensed by the unblinded Investigator and/or unblinded designee will be inventoried and accounted for throughout the study. The study medication must be stored at the appropriate temperature (15°-30°C or 59°-86°F) and in a restricted area with limited access. Temperature excursions are allowed between 2°-60°C (36°-140°F) for a time period not to exceed 72 hours and only during study medication shipment. The unblinded Investigator and/or unblinded designee must maintain an accurate, up-to-date dispensing log for all study medications supplied by the Sponsor. Study medication dispensed for all subjects must be recorded on the drug accountability forms. The study medication dispensing log and remaining drug inventory will be reviewed by the Sponsor-designated unblinded clinical monitor.

The study medication supplied for this study is for use only in subjects properly consented and enrolled into this protocol. Used and unused study medications must be kept in a secure, blinded location physically separated from standard clinic or office drug supplies and with access limited to the unblinded Investigator and/or unblinded designee.

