10.2. Randomization

Subjects will be randomized 1:1:1:1 (0.03 mg active per 2 mL injection: 0.07 mg active per 2 mL injection: 0.23 mg active per 2 mL injection: placebo) to each dose group using a permuted block design stratified by each site. Specific information regarding the use of Medidata Balance to store and implement the permuted block design will be detailed within the statistical analysis plan.

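### A single fixed block size of 8 within site, combined with unblinded site staff who hold the dispensing log, leaves the next allocation partly predictable, and nothing bars those staff from recruitment or Day 1 scheduling.

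*SAP*

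**What the plan says.** Protocol 10.2 assigns subjects 1:1:1:1 "to each dose group using a permuted block design stratified by each site" and leaves the details to the SAP. SAP 2.2 repeats the ratio, "using Medidata Balance with a permuted block design stratified by study site", and adds "A block size of 8 has been selected for this study". No variation in size is described, and the protocol itself gives no block size.

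Protocol 3.2.1 makes part of each site's team unblinded: "The investigational center must identify unblinded personnel who will be responsible for preparing the appropriate dilution of the study medication". These people must also be able to give the injection. Their restriction is that they "must minimize any contact with the subject following the injection and may not perform any study assessments throughout the duration of the study".

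Protocol 8.4 describes the record they keep. The log runs by subject number and has separate entries for active, vehicle, PBS and saline vials. "The unblinded Investigator and/or unblinded designee must maintain an accurate, up-to-date dispensing log for all study medications supplied by the Sponsor".

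Sections 3 and 10 of the protocol give about 445 subjects at up to 40 centres. Screening lasts up to 21 days, and randomisation happens at the Day 1 visit.

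**The concern.** With site-stratified blocks of constant size, the dispensing log is in effect the block history. Once both placebos in a block have been used, everyone left in that block will receive SM04690. Someone who can see this, and who can influence which screened candidate comes to Day 1 next, could match candidates to known allocations.

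The primary endpoint is self-reported WOMAC pain at Week 13, and all three dose comparisons share one placebo arm. If more promising candidates were brought forward into known-active slots, the contrasts would tend to shift in the same direction. Adjustment for baseline would remove little of this, because the power simulation in SAP 2.1 assumes a baseline-to-final correlation of only 0.1.

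**Working it through.** The documents state no predictability figure, so there is none to reproduce.

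**Inputs.** Block size 8, ratio 1:1:1:1 and stratification by site (SAP 2.2); about 445 subjects and up to 40 sites (protocol sections 3 and 10); SD 4 and correlation 0.1 on the 0-20 pain scale (SAP 2.1).

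**Completed block.** Let k be the number of allocations already made in the block.
- Both placebos are used with probability C(6, k-2)/C(8, k) = k(k-1)/56. For k = 2 to 7 this is 0.036, 0.107, 0.214, 0.357, 0.536, 0.750, which sums to 2.
- All six actives are used with probability 1/28 at k = 6 and 1/4 at k = 7, which sums to 2/7.
- Certain slots per block: 2 + 2/7 = 16/7 = 2.286. Share: 2.286/8 = **28.6%**, made up of 25.0% certain SM04690 and 3.6% certain placebo. A simulation of 100,000 blocks also gave 28.6%.
- The exact arm, dose included, is certain at position 8 always and at position 7 with probability 1/7: (1 + 1/7)/8 = 14.3%.

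**Trial level.** 445/40 is about 11 subjects per site, that is, one full block plus three slots: (2.286 + 0 + 0 + 0.036)/11 = **21.1%**. Site numbers and sizes are not given, so these were varied as an assumption. With 40 sites the share is 21.0% for equal enrolment and about 22-23% for unequal enrolment. Over 20 to 40 sites it is about **20-26%**.

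**If the block size is not known.** Take an observer told only that the size is constant and is 4, 8 or 12. The share of allocations certain as active or placebo is:

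| Subjects at site | Observer sees active/placebo | Observer also sees dose |
|---|---|---|
| 8 | 0% | 0% |
| 11 | 0.3% | 0.3% |
| 16 | 8% | 12% |
| 24 | 15% | 17% |

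If the observer considers only sizes 4 and 8, the 11-subject figure returns to about 21%. The result depends strongly on prior knowledge.

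**Illustrative bias (the steering is an assumption).** At 11 subjects per site, expected known-active slots are 2 + 0.036 = 2.036 and expected active subjects are 6 + 3 × 0.75 = 8.25, so the share is 2.036/8.25 = 0.247. SE = 4 × √(1 - 0.1²) × √(2/111) = 0.534.
- Strong: steered subjects improve 2 points more, at half the sites. Bias = 0.247 × 2 × 0.5 = **0.25 points**. Shift = 0.247/0.534 = 0.46 SE. Two-sided error = Φ(-2.42) + Φ(-1.50) = **7.5%** instead of 5%.
- Mild: 1 point at 10% of sites. Bias = 0.247 × 1 × 0.1 = 0.025 points, with error still about 5.0%.
- With completed blocks only, the share is 2/6 = 0.33. The strong case becomes 0.33 points and about 9.6%.

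**Effect of varying sizes (random 4, 8 and 12).** For an observer who knows the mix, at sites of 8 to 24 subjects, certain active/placebo knowledge falls to about 1-3% if only active/placebo is seen, and to 1-7% if dose is also seen. The best guess of the exact arm barely moves: it is right 42% of the time at 11 subjects and 47% in completed blocks now, against 41.5-45.1% with varying sizes.

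**The case against.** The case on the other side is substantial, and most of it stands.

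- **Certainty needs the block size.** It is printed only in the SAP, and nothing in the documents gives site staff the SAP. At 11 subjects the log alone reveals almost nothing to someone entertaining sizes of 4, 8 and 12. This makes the 20-29% figures upper bounds.
- **The before-and-after comparison favours the fix.** It assumes that the current size is known. If it is not, a site of 11 has 0.3% certain slots today, which varying blocks would not improve.
- **Eligibility is partly protected.** The bar in Protocol 3.2.1 covers any study assessment, and Protocol 6.1 and 6.2 describe the eligibility work as procedures and assessments. A reader might infer that unblinded staff are free to make the judgement-based exclusions, such as knee misalignment. The text does not support that: the bar plausibly covers those examinations, and Kellgren-Lawrence grade is read centrally. Recruitment and Day 1 timing remain uncovered.
- **Re-screening is a weak route.** The reasons allowed include "being unable to comply with study procedures due to administrative convenience", but Protocol 3.2.3 permits it once, for a transient reason, with new consent and all screening repeated.
- **Seeing every allocation is an inference.** Protocol 8.4 requires a complete log, but no sentence says that one person sees all of it.
- **Timing.** The synopsis expects the last subject to complete in April 2017 after 52 weeks of follow-up, so randomisation would end around April 2016. There may be no unopened blocks left.

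What survives is narrower: the block size is constant, the log shows active versus placebo, and no sentence keeps its holders out of recruitment or scheduling.

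**Conclusion.** The point holds as a cheap improvement to allocation concealment, not as an error or contradiction in the plan. The design allows certain knowledge of active versus placebo for 28.6% of slots in completed blocks and about 20-26% of randomisations overall. This rests on two assumptions: that a log holder knows or infers the block size, and the assumed spread of site sizes.

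Two stronger readings should be resisted. A reader might infer that staff know the next allocation in 29% of all randomisations. That is the completed-block ceiling, and it requires a number that the protocol does not give to sites. A reader might also infer that the Week 13 pain comparison is biased. Nothing in the documents shows that subjects are steered. The 0.25 points and 7.5% error require every known-active slot at half the sites to be filled with subjects who improve 2 points more, and milder steering has no material effect.

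**What to change.** 1. **SAP 2.2.** Replace the single size with randomly varying block sizes within site (for example 4, 8 and 12) for blocks not yet opened. State that the sizes and the list are held only by the unblinded randomisation statistician. If the size would otherwise be known, this removes most certain knowledge, though it hardly changes best-guess accuracy.
2. **Protocol 3.2.1.** Add that personnel who prepare or inject study medication, or who hold the dispensing log, take no part in recruitment, eligibility decisions or scheduling of Day 1 visits. This closes the remaining route whether or not the block size is known, and is the more useful of the two changes.

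Cost: one setting in the existing randomisation system and one sentence in each document, with no extra subjects or staff. The downside is slightly more arm imbalance at sites that stop part-way through a larger block. If randomisation is already complete, the block change no longer applies.

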2.3. Study Medication Dosing

Three strengths of SM04690 injectable suspension and placebo will be used in this study:

- SM04690 0.03 mg in 2-mL Injectable Suspension
- SM04690 0.07 mg in 2-mL Injectable Suspension
- SM04690 0.23 mg in 2-mL Injectable Suspension
- SM04690 0 mg in 2-mL Injectable Suspension; placebo (phosphate buffered saline)

3. STUDY OUTCOME MEASURES

3.1. Safety Outcome Measures

TEAEs will be presented in summary tables and categorized by seriousness and toxicity severity grade. While all TEAEs will be considered as related to study product, the investigator's assessment of relatedness will be analyzed for informational purposes. TEAEs will also be summarized according to MedDRA dictionary terms, including system organ class and preferred term.

3.2. Efficacy Outcome Measures

Knee pain and function will be assessed by the subject using the WOMAC Index. Disease activity will be assessed by the Patient Global Assessment of Disease Activity and the Physician Global Assessment of Disease Activity. Overall HRQOL will be assessed with the SF-36 questionnaire which provides scores for eight scales (physical functioning, role-physical, bodily pain, general health, vitality, social functioning, role-emotional, mental health) and two summary measures (physical health, mental health). JSW will be assessed with X-Ray imaging of the target knee at Week 26 and 52.

3.2.1. Western Ontario and McMaster Universities Arthritis (WOMAC) Index

The WOMAC NRS3.1 instrument is a patient reported outcome measure to assess the symptoms of OA. Subjects will be asked to complete the WOMAC instrument based on their symptoms in the target knee.

The WOMAC consists of 24 questions in three domains: physical function (17 questions), pain (5 questions) and stiffness (2 questions). The response for each question in the NRS format ranges from 0 to 10. Each domain subscore as well as a total score are calculated by adding together the numerical responses. Subsequently, the WOMAC NRS3.1 ranges from 0 to 240 total points.

If any response is missing, the score for that domain (i.e. physical function, pain, or stiffness) as well as the WOMAC Total score will not be able to be calculated.

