5.2. Handling of Missing Data

Multiple imputation will be utilized for the primary and secondary analyses. Missing data will be imputed based upon the observed data for each outcome under the missing at random (MAR) assumption following the paradigm first developed by Rubin (Schafer 1999). The imputation will adjust for the outcome’s baseline data in a regression model with data imputed independently for each timepoint; any missing baseline data will also be imputed. A total of 10 imputation datasets will be created and analyzed based upon accepted convention (Schafer 1999). Error estimates of the multiple imputation itself as well as an overall summary of the efficacy analysis will be averaged across the 10 imputed datasets based upon Rubin’s paradigm.

Specifically, let Q denote the imputed mean of an efficacy outcome Y subject to missing data at a given timepoint, where the estimate of that mean for any i^{th} imputation would be defined as function of both observed and missing data such that

$$\widehat{Q}^{(i)} = E\left(Q^{(i)} | Y_{observed}, Y_{missing}^{(i)}, Y_{Baseline}, I(Group)\right), i = 1, \dots, 10.$$

After all 10 datasets have been imputed, the overall estimate of Q is a simple average defined as

$$\bar{Q} = \frac{\sum_{i=1}^{10} \widehat{Q}^{(i)}}{10}.$$

For this analysis using 10 imputed datasets, the variance of \bar{Q} is defined as

$$Var(\bar{Q}) = 1.1B + \bar{U}$$

where B is the between imputation variance and U is the within imputation variance:

$$B = \frac{1}{9} \sum_{i=1}^{10} (\widehat{Q}^{(i)} - \bar{Q})^2;$$

$$\bar{U} = \frac{\sum_{i=1}^{10} U^{(i)}}{10}.$$

Imputations will be performed with a seed of 201610141.

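### One blank WOMAC item voids the domain and the Total, so items answered at the visit are discarded; prorating would be a cheap gain, mainly for function and Total

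*SAP*

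**What the plan says.** SAP 3.2.1 describes the instrument: 17 function, 5 pain and 2 stiffness items, each scored 0 to 10 and summed. Its missing-item rule is this: "If any response is missing, the score for that domain" cannot be derived, "as well as the WOMAC Total score will not be able to be calculated". Neither document contains a proration or item-level rule that softens this.

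SAP 5.2 applies multiple imputation (10 datasets, missing at random) to the primary and secondary analyses. It adjusts for the outcome's baseline "in a regression model with data imputed independently for each timepoint", and it also imputes missing baselines. The formula in that section conditions on treatment group as well. Items answered at the visit and scores from other visits are not in the model.

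SAP 1.3 lists WOMAC Total and the OMERACT-OARSI responses as exploratory, so they fall outside the stated scope of imputation.

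For power, SAP 2.1 assumes for function: "Correlation between baseline and final function score is 0.1". It makes the same assumption for pain.

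SAP 5.3 defines the WOMAC baseline as the last value recorded before injection. Protocol 3.3.4 exempts Screening from the 24-hour hold on pain and OA medication.

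**The concern.** A subject who answers 16 of 17 function items has given nearly all the information in the score. The plan treats that subject like one who did not attend, and fills the gap from a baseline that, on the SAP's own assumption, explains 1% of the final score's variance.

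Four things are at stake:

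- **Precision.** It is lost mainly for function, which has the most items of the imputed domains. Function at Week 13 for the 0.07 mg dose is H4 in the fixed sequence of SAP 8.2.1. If H4 fails, the 17 tests after it (21 − 4) become exploratory.
- **Total.** A single blank stiffness item voids it even when pain and function are complete, and no imputation is stated for it. The OMERACT-OARSI responses draw on pain and function and share that gap.
- **Baseline.** If a blank on Day 1 makes the score incalculable, baseline may fall back to the Screening value, which was taken without the medication hold, or may be imputed. Baseline conditions could then differ between subjects.
- **Tipping-point analysis (SAP 5.2.1).** Subjects with 4 of 5 pain items answered would count among the missing, which blurs a check meant for data that were never observed.

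**Working it through.** **1. Instrument structure (SAP 3.2.1).** 17 + 5 + 2 = 24 items and 24 × 10 = 240 points, as stated. With one blank, the answered items discarded are 16 (function), 4 (pain), 1 (stiffness) and 23 (Total).

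**2. The SAP's power figures (SAP 2.1).** Inputs: 100 per arm, two-sided 5% (SAP 8.1.1), correlation 0.1.

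- Function: difference 19.5 − 13.5 = 6.0, final SD 15, residual SD 15 × √0.99 = 14.925.
- Pain: difference 5.8 − 3.5 = 2.3, final SD 4, residual SD 4 × √0.99 = 3.98.

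Power = Φ(difference / (residual SD × √(2/n)) − 1.96).

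- Function: Φ(2.843 − 1.96) = 81.1%. A 20,000-replicate ANCOVA simulation gives 80.5%. The SAP states 78.5%.
- Pain: Φ(4.086 − 1.96) = 98.3%. Simulation gives 98.2%. The SAP states 95.8%.

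The SAP's figures do not reproduce exactly. That is a separate matter; the comparisons below start from the recomputed values.

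**3. Information kept and lost.** Baseline explains 0.1² = 1% of final-score variance. With equal inter-item correlation ρ, m of k items explain m(1 + (k−1)ρ) / [k(1 + (m−1)ρ)] of the full-score variance. The documents give no ρ, so I assume 0.3 to 0.8.

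- Function, 16 of 17: 92.8/93.5 = 99.3% at ρ = 0.3, and 99.9% at ρ = 0.8.
- Pain, 4 of 5: 8.8/9.5 = 92.6% at ρ = 0.3, and 98.8% at ρ = 0.8.

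**4. Scores voided per visit.** The documents give no skip rate. For an assumed independent rate p per item, the voided share is 1 − (1 − p)^k.

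| p per item | Pain (k = 5) | Function (k = 17) | Total (k = 24) |
|---|---|---|---|
| 0.25% | 1.2% | 4.2% | 5.8% |
| 0.5% | 2.5% | 8.2% | 11.3% |
| 1% | 4.9% | 15.7% | 21.4% |

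Blanks that cluster on the same forms void fewer scores at the same p.

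**5. Effect on power.** I count a voided score as adding no information, which is reasonable when baseline explains 1%. The effective n is then n × (1 − voided share).

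- Function, 100 per arm, p = 0.5%: n = 91.8, power 77.8% against 81.1%. At p = 0.25% it is 79.5%, and at 1% it is 74.2%.
- Function, 445/4 ≈ 111 per arm, p = 0.5%: n = 101.9, power 81.9% against 85.0%, before dropout.
- Pain, 100 per arm, p = 0.5%: n = 97.5, power 98.1% against 98.3%.

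**6. After proration with the thresholds under fix.** At p = 1%, pain is voided only if two or more items are blank: 1 − 0.99⁵ − 5 × 0.01 × 0.99⁴ = 0.1%. Function needs four or more blanks: about 2380 × 0.01⁴ × 0.99¹³ = 0.002%. Stiffness needs both: 0.01² = 0.01%.

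**The case against.** The rule is explicit, pre-specified and consistent with the rest of the plan. Voided primary and secondary scores go to multiple imputation with Rubin's variance, and the primary analysis has a tipping-point check for significant doses. Proration is itself a single imputation within the domain, needs its own assumption, and does not carry its uncertainty forward. All of this stands, and it is why the point concerns efficiency. None of it recovers items that the subject answered and the rule discards.

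The size is assumed, and independence is unfavourable to the plan compared with clustered blanks. That also stands. About 111 per arm are randomised, so an 8.2% loss still leaves about 102, above the simulated 100; but dropout draws on the same margin.

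Subject and staff both sign the form (Protocol 5.8), monitors verify all eCRFs against source (Protocol 11.2), and queries are closed before unblinding (SAP 5.1). A blank may be noticed at the visit, but no passage requires a check that all 24 items are answered, and later verification cannot supply a missing answer.

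A reader might infer that voided scores are imputed from baseline alone, or that a voided Total is imputed too. Neither is supported: the formula in SAP 5.2 also conditions on treatment group, and imputation is stated only for primary and secondary analyses, while Total is exploratory.

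**Conclusion.** The point holds as a cheap efficiency improvement. The rule discards answered items and, for primary and secondary endpoints, replaces the score with an imputation that uses none of them. The cost falls mainly on function and Total: at an assumed 0.5% independent skip rate, 8.2% of function scores and 11.3% of Totals are voided per visit, and function power drops by about three points, whether from 81% at 100 per arm or from 85% at about 111.

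It would be tempting to conclude that the primary endpoint is materially weakened or that the results would be biased. The documents support neither. Pain power moves by about 0.2 points at that rate, and nothing shows that skipping differs by arm or depends on outcome. I have put no figure on the baseline effect; SAP 5.3 does not say how a Day 1 form with a blank item is handled, so the fall-back to Screening is a possibility and not a stated rule.

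The figures rest on the assumed skip rate, on independence across items, on the SAP's correlation of 0.1, and on the assumed inter-item correlations of 0.3 to 0.8.

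**What to change.** Amend SAP 3.2.1 before the interim unblinding:

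- Prorate a domain as the mean of its answered items times its number of items when at least 4 of 5 pain, 14 of 17 function or 1 of 2 stiffness items are answered. Otherwise the domain is missing and SAP 5.2 applies within its stated scope.
- Define Total as the sum of the three domain scores.
- Apply the rule at baseline and at every follow-up visit.
- Report the number of prorated scores by arm.
- Keep the complete-item rule as a sensitivity analysis.

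The thresholds are my proposal; neither document gives any. Protocol 5.8 calls the instrument proprietary, so the sponsor should check them against any scoring guidance it holds.

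The cost is a short SAP paragraph and a few lines of derivation code. The downside is a small assumption that skipped items resemble the answered ones, with the uncertainty of the filled item not carried forward. That assumption is weakest for stiffness, where one item stands in for two. If blanks prove rare, almost nothing changes.
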